## 2.2 Violations and deviations

AstraZeneca use International Conference on Harmonization (ICH) E3 terminology for protocol deviations (PDs), which are all important deviations related to study inclusion or exclusion criteria, conduct of the trial, participant management or participant assessment. All protocol deviations (PDs) identified during monitoring of the study are recorded in the clinical trial management system (CTMS). Important protocol deviations (IPDs) are a subset of protocol deviations that may significantly impact the completeness, accuracy, and/or reliability of the study data or that may significantly affect a participant's rights, safety, or well-being.

The reporting of PDs and hence the CTMS changed on 16MAY2022. The main changes were the addition of the flag identifying the IPDs as well as changes to the PD categories.

A detailed description of how PDs and IPDs are collected and identified is referenced in the Protocol Deviation Management Plan.

The final list of IPDs will be documented prior to unblinding the study data for the final DBL and re-visited if required once the study is unblinded (for example, incorrect IP administration). This list may include, but not limited to the following categories:

- Inclusion Criteria Deviations
- Exclusion Criteria Deviations
- Discontinuation Criteria for study product met but participants not withdrawn from study treatment
- Discontinuation Criteria for overall study withdrawal met but participant not withdrawn from study
- Deviations from IP management and administration
- Prohibited Medications Taken
- Deviations related to study procedure such as informed consent
- Other Important Deviations
  - Scheduled study assessments not done or incorrectly performed which could impact the primary or key secondary endpoints
  - Unblinding of treatment assignment for reasons unrelated to participant safety
  - Other severe non-compliance (such deviations will be clearly described in the CSR)

The IPDs will be listed including the full PD text as entered in the CTMS by site staff or CRAs and summarised by randomised treatment group including the old and new categories

depending on when the PD was reported (before or after 16MAY2022). IPDs will also be summarised separately by whether they are due to COVID-19 or not.

None of the deviations will lead to participants being directly excluded from the analysis sets described in section 2.1. The only exception being for the PK analysis set, if the deviation is considered to significantly impact upon PK assessments. That is:

- If a participant randomised to an active treatment receives only placebo, then such participant would be excluded from the PK analysis set.
- If a participant randomised to placebo receives only active treatment, then such participant would also be excluded from the PK analysis set (per protocol PK samples from participants randomised to placebo are not to be analysed).
- If a participant randomised to placebo receives only placebo, but has any post-baseline PK data available, such participant will be excluded from the PK analysis set.
- If a participant randomised to an active treatment receives an incorrect dose or placebo during the treatment period then such participant would be included in the PK analysis set, but PK assessment(s) after such dose would be excluded from summary outputs.
- Participants with missed IP dose will be included in the PK analysis set, but such participants will be discussed case by case prior to unblinding to agree on the PK assessments use. The generic rule would be to not include assessment(s) made after the missed dose in summary outputs. Such data would be set to missing on the ADaM level so that there is traceability (but will be included in the SDTMs).
- Participants that don't receive a full volume of the IP will be included in the PK analysis set if more than 80% of the volume was administered. If less than 80% of the volume was administered, then such cases will be reviewed prior to unblinding and handled case by case.

In addition, if a participant does not receive IP, this would lead to their exclusion from the safety set. A per protocol analysis excluding participants with specific important protocol deviations is not planned.

### 3 PRIMARY AND SECONDARY VARIABLES

#### 3.1 General principles

##### 3.1.1 Missing data

Unless specifically detailed otherwise, the attributable estimand approach will guide the analysis and summary of primary and key secondary variables, whereas other variables will be analysed and/or summarised using available data only.

For more information on handling of missing data and imputation refer to section 4.1.1.

##### 3.1.2 Baseline

In general, baseline will be the last non-missing assessment value obtained prior to the first dose of randomised study treatment. If a participant is randomised and not treated, then baseline would be the last non-missing assessment prior or on the day of randomisation (Day 1).

However, for the primary endpoint of NRS pain score, **CCI**, the baseline is defined as the average (mean) of daily scores recorded during the 7-day period immediately prior to randomisation (Day -7 to Day -1, inclusive). At least four of the seven daily scores need to be recorded by the participant to obtain a valid baseline value for statistical analyses.

In addition, the baseline for rescue medication is defined as the sum of daily use recorded during the 7-day period immediately prior to randomisation (Day -7 to Day -1, inclusive).

##### 3.1.3 Change and percentage change from baseline

In general, change from baseline outcome variables are computed as:

(post-baseline value - baseline value)

In general, percent change from baseline outcome variables are computed as:

$((\text{post-baseline value} - \text{baseline value}) / (\text{baseline value})) * 100$

However, for the primary endpoint, the change from baseline is defined as the weekly average of the daily NRS pain scores at Week x minus the baseline weekly average NRS pain score. The derivation of the weekly average of the daily NRS pain scores at Week x is described in section 3.2. In addition, for primary and key secondary endpoints the percent change from baseline is expressed in terms of improvement as follows:

$((\text{baseline value} - \text{Week 12 value}) / (\text{baseline value})) * 100$

### **3.1.4 Early termination visit**

Assessments associated with an early termination of IP are the same as those for EOT (Week 12) visit. Consequently, summaries presented by visit will not differentiate whether the Week 12 assessments correspond to the EOT or the ET visit. The exceptions are the primary endpoint, secondary endpoints, **CCI**, TNSn and DSIS for which the handling of the data associated with ET visit can be found in sections 3.2, 3.3, 3.6.4 and 3.5.1.1 respectively.

### **3.1.5 Study periods**

The below definitions of study periods are defined as per the protocol and study design [Figure 1](#).

#### **3.1.5.1 Pre-treatment period**

The pre-treatment period is defined from signed informed consent until Day 1 prior to first administration of study treatment.

#### **3.1.5.2 Treatment period**

The treatment period is defined from the first administration of study treatment (Day 1) through to the Week 12 (EOT/ET) visit, regardless of when IP is discontinued.

#### **3.1.5.3 Follow-up period**

The follow-up period starts after Week 12 (EOT/ET) visit and ends with end of study participation.

### **3.1.6 Exposure related periods**

These periods are defined in terms of safety assessments and exposure to IP. If the assessment is not associated with the time and hence it cannot be determined whether the assessment on Day 1 is prior to or after the first dose of IP, then it will be assumed that assessment is after the IP unless otherwise stated.

#### **3.1.6.1 Prior treatment**

Prior treatment is defined from signed informed consent until Day 1 prior to first IP administration. In cases where the participant is randomised and IP is not administered then all assessments on Day 1 would be considered prior treatment.

#### **3.1.6.2 On treatment**

On treatment is defined from the day and time of first IP administration throughout to the last IP administration +14 days, based on MEDI7352 half-life of 3-4 days. Participants that are randomised and do not receive IP will not be part of 'on treatment' period.

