### Treatments and treatment duration:

The study consists of a screening period of up to 45 days (one or more visits), a 12-week double-blind treatment period (10 scheduled visits), and a 24-week follow-up period (3 scheduled visits and 4 phone calls).

After screening and confirmation of eligibility criteria, eligible participants will be randomised on Day 1 at a 1:1:1:1:1 ratio to receive MEDI7352 doses or placebo. Participants will receive a total of 6 CCI injections (every 2 weeks [Q2W] at Day 1, weeks 2, 4, 6, 8 and 10):

- Cohort 1: MEDI7352 CCI
- Cohort 2: MEDI7352 CCI
- Cohort 3: MEDI7352 CCI
- Cohort 4: MEDI7352 CCI
- Cohort 5: Placebo

Participants who complete the treatment period will come in for their end-of-treatment (EOT) visit at Week 12 and then enter the follow-up period. Participants who permanently discontinue investigational product (IP) will be asked to complete study assessments at the early termination (ET) visit (Week 12 assessments) as soon as possible and then enter the follow-up period. All participants are expected to complete the EOT/ET visit and the 24-week follow-up period.

The study incorporates two interim analyses, detailed in section 5.

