### 3.1.6.3 Post treatment

Post treatment is defined from last IP+15 days through to the date of last study assessment.

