#### 4.2.6.4 Laboratory results

Tables with descriptive summaries (mean, SD, median, minimum, and maximum) of actual (absolute) values and changes from baseline values will be produced for each treatment group at each visit. Tables will be produced for tests specified in section 3.6.8 except for urine drug screen, urine pregnancy test, serology, and endocrinology. Participants with abnormal results of these tests except for urine pregnancy test will be only listed including all available results.

Central laboratory reference ranges will be used for the identification of abnormalities. Shift tables will be produced for the same parameters for which summary tables will be produced with the exception of urinalysis to display low, normal, and high values.

The shift tables will present baseline and maximum/minimum on-treatment value, as applicable for each parameter and will include participants with both baseline and post-baseline data. The exception would be Haemoglobin A1c that is evaluated only at baseline and Week 32 hence this shift table will present baseline and maximum/minimum value during the study.

For urinalysis parameters collected as for example: Negative, Small, Moderate or Large, shift tables from baseline to maximum value during treatment will be provided. This will apply to bilirubin, blood, leucocytes, glucose, protein and ketones. Key participant information table listing only participants and assessments with abnormal values will be produced.

Laboratory values will also be presented as box plots, for absolute values and changes from baseline. All protocol defined visits will be summarised.

Each plot will show the following details:

- Mean (symbol within each box)
- Median (horizontal line within each box)
- Q1 and Q3 (bottom and top of each box)
- Whiskers extending to the most extreme observation within 1.5 times the interquartile range from the nearest quartile.
- Outliers outside the whiskers displayed individually.
- Reference ranges shown as dotted lines on the analysis value plots, not relevant to the change from baseline plot. If more than one reference range is available for an assessment (example: due to gender differences) then the narrowest range will be used in the graph.

The plots will be prepared for each test within the laboratory categories:

- Haematology: hemoglobin, hematocrit, RBC count, platelet count (or estimate), WBC count, WBC differential

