#### 4.2.6.4.1 Liver enzyme elevations and Hy's law

Liver function laboratory tests assessments (scheduled and unscheduled) up to 30 days after the last dose of study treatment will be considered.

The following summaries will include the number (%) of participants with at least one post-baseline liver function assessment who have:

- Elevated ALT, AST and total bilirubin as
  - ALT  $\geq 3\times$  to  $<5\times$ ,  $\geq 5\times$  to  $<10\times$ ,  $\geq 10\times$  to  $<20\times$ ,  $\geq 20\times$  upper limit of normal (ULN)
  - AST  $\geq 3\times$  to  $<5\times$ ,  $\geq 5\times$  to  $<10\times$ ,  $\geq 10\times$  to  $<20\times$ ,  $\geq 20\times$  ULN
  - Total bilirubin  $\geq 2\times$  ULN
  - ALT or AST  $\geq 3\times$  to  $<5\times$ ,  $\geq 5\times$  to  $<10\times$ ,  $\geq 10\times$  to  $<20\times$ ,  $\geq 20\times$  ULN
  - ALT or AST  $\geq 3\times$  ULN and total bilirubin  $\geq 2\times$  ULN (Potential Hy's law): The onset date of ALT or AST elevation should be prior to or on the date of total bilirubin elevation.

Percentages will be based on the number of participants who have at least one measurement available.

To identify potential Hy's Law cases, a listing of participants who have ALT or AST  $\geq 3\times$  ULN and total bilirubin  $\geq 2\times$  ULN (not necessarily at the same time) following first dose of study treatment will be provided.

A shift table will also present maximum ALT and AST observed values by maximum total bilirubin observed value, expressed as multiples of ULN. Categories will be included for:

- ALT  $<3$ ,  $\geq 3\times$  to  $<5\times$ ,  $\geq 5\times$  to  $<10\times$ ,  $\geq 10\times$  to  $<20\times$ ,  $\geq 20\times$  ULN
- AST  $<3\times$ ,  $\geq 3\times$  to  $<5\times$ ,  $\geq 5\times$  to  $<10\times$ ,  $\geq 10\times$  to  $<20\times$ ,  $\geq 20\times$  ULN
- Total bilirubin  $<2\times$ ,  $\geq 2\times$  ULN

Key participant information table of participants with potential Hy's law will be produced.

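### The on-treatment window closes on the nominal Week 12 day with no tolerance, so end-of-treatment laboratory results taken 15 or more days after the last dose fall out of the on-treatment shift tables

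*SAP*

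**What the plan says.** The schedule is in SAP section 1.2, under treatments and treatment duration. Injections are given "every 2 weeks [Q2W] at Day 1, weeks 2, 4, 6, 8 and 10". On the end of treatment it says "Participants who complete the treatment period will come in for their end-of-treatment (EOT) visit at Week 12". Those who stop IP permanently are asked to attend an early termination (ET) visit promptly, but no day is fixed for it.

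The exposure-related periods are in section 3.1.6, which ties them to safety assessments:

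- Section 3.1.6.2: "On treatment is defined from the day and time of first IP administration throughout to the last IP administration +14 days". The reason given is a half-life of 3 to 4 days.
- Section 3.1.6.3: "Post treatment is defined from last IP+15 days through to the date of last study assessment".

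Section 4.2.6.4 then states: "The shift tables will present baseline and maximum/minimum on-treatment value, as applicable for each parameter". Haemoglobin A1c is the only exception named; its shifts use the whole study. In the same section the urinalysis shifts, and in section 4.2.6.5 the vital-sign shifts, use the extreme value during treatment and do not say how that is bounded.

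Two other windows matter here. Section 3.1.5.2 runs the treatment period "through to the Week 12 (EOT/ET) visit, regardless of when IP is discontinued". Section 4.2.6.4.1 says of liver tests: "Liver function laboratory tests assessments (scheduled and unscheduled) up to 30 days after the last dose of study treatment will be considered".

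**The concern.** The Week 12 laboratory sample is the planned reading after all six doses, and the ET sample is its counterpart for those who stop early. A table of worst on-treatment values should have a settled rule for including them. Under the current wording, a day or two of scheduling variation between the last dose and the visit can decide it. Section 3.1.8 applies no visit windowing unless otherwise specified, and the SAP makes no exception for EOT or ET results, so nothing absorbs that variation.

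Two practical consequences follow:

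- A participant's Week 12 value can appear in the by-visit table and be ineligible for the shift table.
- An ALT value from day 16 after the last dose would count in the liver tables but not in the chemistry shift table.

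For urinalysis and vital signs, two programmers could reasonably choose different periods.

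**Working it through.** **Inputs.** Last planned dose at Week 10 and EOT visit at Week 12 (section 1.2). Window of last IP +14 days (3.1.6.2), with post treatment from +15 days (3.1.6.3). Day labels are 7 × week: section 3.1.8 labels Week 10 as Day 70 and Week 32 as Day 224, so Week 12 is Day 84.

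**Nominal case.** 70 + 14 = 84, the Week 12 day itself. Post treatment starts on Day 85. Slack = 14 − (84 − 70) = 0 days. Using the relative study day of section 3.1.7, which adds 1, the days are 71 and 85 and the gap is still 14.

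**General rule.** Let the Week 10 dose be shifted by *a* days and the Week 12 visit by *b* days. The visit is post treatment if (84 + b) − (70 + a) > 14, that is, if b > a.

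| Last dose | Visit | Days since last dose | Class |
|---|---|---|---|
| Day 70 | Day 84 | 14 | on treatment |
| Day 70 | Day 85 | 15 | post treatment |
| Day 71 (one day late) | Day 85 (one day late) | 14 | on treatment |
| Day 69 (one day early) | Day 84 (on time) | 15 | post treatment |
| Day 56 (Week 8; Week 10 missed) | Day 84 (on time) | 28 | post treatment |

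An ET visit follows the same clock: it is on treatment up to day 14 after the last dose and post treatment from day 15.

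**Link to the tables.** Section 4.2.6.4 does not cite 3.1.6.2, but it uses the term defined there, and section 3.1.6 says those periods are for safety assessments. Read that way, a post-treatment result is not eligible as the on-treatment maximum or minimum for haematology, chemistry or coagulation.

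**Size.** Visit windows are not in this document, so the affected share cannot be computed. The following is an illustration only. If dose and visit shifts were independent and uniform over ±k days, P(b > a) = (1 − 1/(2k+1))/2 = k/(2k+1). This gives 2/5 = 40% for k = 2, 3/7 = 43% for k = 3 and 5/11 = 45% for k = 5. If sites book Week 12 from the actual Week 10 date, the shifts move together and the share falls. A dropped value changes a shift table only if it is that participant's extreme and lies in a different category from the remaining values.

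**The case against.** The strongest reply is that only one presentation is affected. Section 3.1.4 keeps EOT and ET results together as Week 12 in by-visit summaries. Section 4.2.6.4 summarises and box-plots all protocol-defined visits. The abnormal-result listings show every available result for an affected test, and liver tests have their own tables with a 30-day window. Safety analysis is descriptive only. All of this stands, and it limits the point to a modest one.

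A reader might infer more than the documents support:

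- *That any Week 12 visit one day late drops out.* The clock runs from the actual last dose, so a late visit after an equally late dose stays in.
- *That ET results are generally lost.* An ET visit within 14 days of the last dose stays in. ET assessments done at the next due dosing visit fall on day 14 on the nominal schedule. An abnormal result that caused the stop was obtained before the stop and may already be on treatment.
- *That adverse events first noticed at a late visit become post treatment.* Section 3.6.1 goes by onset, and the main tables count treatment-emergent events to the end of study participation.
- *That the SAP contradicts itself.* Study periods, exposure periods and the liver window are separate definitions for separate outputs. What is missing is a statement of which one governs the urinalysis and vital-sign shifts.
- *That abnormalities are understated more in some arms.* Differential loss is possible, but nothing here shows it.
- *That the half-life rules out 14 days.* Fourteen days is 14/4 = 3.5 to 14/3 = 4.7 half-lives, leaving about 9% to 4% of drug. The document sets no benchmark that this fails.

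It can also be said that a longer window would label some low-exposure values as on treatment. That is true and is the real cost of the change.

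**Conclusion.** The point holds in limited form. The window equals the planned interval between the last dose and the EOT visit. EOT or ET laboratory results from day 15 onward after the actual last dose are therefore ineligible for the haematology, chemistry and coagulation shift tables. This happens when the visit slips more than the dose did, when the Week 10 dose was early or missed, or when the ET visit is held late. For urinalysis and vital signs the governing period is unstated, so the effect there is ambiguous.

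The conclusion assumes that the shift-table term carries its section 3.1.6.2 meaning. The number of participants affected is unknown. No effect on efficacy results or on the treatment-emergent adverse event count follows. It is a cheap improvement to a safety display and does not threaten the trial's conclusions.

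**What to change.** For the laboratory, urinalysis and vital-sign shift tables, take the maximum or minimum over results from first IP up to the later of last IP +14 days and the Week 12 (EOT/ET) visit. Name that period in sections 4.2.6.4 and 4.2.6.5 and in each table's footnote. The section 3.1.5.2 treatment period already ends at that visit, so the change uses an existing concept. Haemoglobin A1c and the 30-day liver tables stay as they are. The adverse event tables by period go by onset date and can keep the section 3.1.6 definitions.

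The cost is one analysis definition and a rerun of the affected programs, with no change to data collection. The downside is that a few values taken well after the last dose would count, for example at 28 days when Week 10 was missed. A footnote giving the number of participants whose extreme value came more than 14 days after the last dose would make this visible.

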### 3.1.6.3 Post treatment

Post treatment is defined from last IP+15 days through to the date of last study assessment.

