#### 3.6.1 Adverse events

AEs and serious AEs (SAEs) as defined in the protocol appendix C will be collected from the screening, throughout the study, and including the follow-up period. The Medical Dictionary for Regulatory Activities (MedDRA) will be used to code the AEs, using the latest version. AEs will be graded according to the Common Terminology Criteria for AEs (CTCAE version 5).

A treatment emergent adverse event (TEAE) is defined as:

- any AE with an onset at the time of or following the start of study treatment through the end of study participation as per DS page in eCRF;

- any AE starting prior to the start of study treatment administration but increasing in severity at the time of, or following, the start of study treatment through end of study participation as per DS page in eCRF.

Any AE occurring before the first dose of study treatment and without worsening after the first dose will be included in the data listings but will not be included in the AE summary tables.

The causal relationship between IP and each AE will be recorded. For SAEs, causal relationship will be assessed for other medication and study procedures.

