##### **4.2.6.1 Adverse Events**

Summary tables will include TEAEs as defined in section 3.6.1, unless otherwise specified.

An AE overview summary table will be produced showing the number (%) of participants with at least one AE in each of the following categories:

- Any AE
- Any AE with an outcome of death
- Any SAE

- Any AE leading to discontinuation of study treatment
- Any severe AE
- Any AESI
- Any AE leading to withdrawal from study

For all categories above, the number (%) of participants with at least one causally related AE in that category will also be provided.

An additional table will be produced showing the incidence of participants with the following type of adjudicated events:

- RPOA (type 1 and 2)
- SIF
- Primary osteonecrosis,
- Pathological fracture

The number of participants treated per treatment group will be used as the denominator to calculate percentages.

Summary tables will be produced by MedDRA SOC and PT for the following categories:

- AEs
  - By age group as defined in section 4.2.8
  - By sex
  - By periods as defined in section 3.1.6.
  - By ADA categories as defined in section 3.4.2
- Severe AEs
- By periods as defined in section 3.1.6. Causally related AEs and SAEs
  - By periods as defined in section 3.1.6.
- SAEs with outcome death
- SAEs
  - By periods as defined in section 3.1.6.
  - By ADA categories as defined in section 3.4.2
- AEs leading to discontinuation of study treatment
- AESIs
  - By periods as defined in section 3.1.6
  - Separate table to be provided for each AESI category as defined in section 3.6.1.1
    - By periods as defined in section 3.1.6
    - Joint related AESI table by study periods will also include the exposure adjusted rates, where AE event rate (per 100 participant years) is defined as the number of

participants with that AE divided by the total number of days at risk for AEs across all participants in given treatment arm and multiplied by  $365.25 \times 100$  to present in terms of per 100 participant years.

- Most common non-serious AEs defined as AEs occurring in at least 5% of participants overall (in total column). For each SOC/PT, the number (%) of participants reporting at least one event at each level of summarisation will be presented. Participants with multiple occurrences of the same AE, the event will only be counted once per SOC/PT. Those will be sorted by international order for system organ class and in alphabetical order for preferred term.

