## 6 CHANGES OF ANALYSIS FROM PROTOCOL

- The final analysis and its reporting will be split to two deliverables that would be supported by two database locks at timepoints specified in section 1. This is to evaluate the efficacy data once all participants complete the treatment period as it is not anticipated that this data will change rather than waiting once all participants complete the study especially after the follow-up period was extended from 12 to 24 weeks.
- Single imputation will be performed only for the primary and key secondary endpoints as it is not meaningful to perform the single imputation for endpoints that will only be summarised.
- The sequentially rejective multiple comparison approach includes not just pairwise comparisons, but also the dose response curve for the WOMAC pain subscale score. In addition, MCP-MOD analyses of the remaining key secondary endpoints will not be performed.
- Additional supplementary analyses not specified in the protocol were added for comparative purposes within the industry. Those are: ANCOVA analysis of the primary endpoint and WOMAC pain subscale score key secondary endpoint using singly imputed LOCF cases as well as ANCOVA analysis of the WOMAC pain subscale score key secondary endpoint using multiply imputed cases that were imputed using the sampling from normal distribution approach.
- The protocol presents the concomitant medication and therapies as a safety endpoint. However, this data does not necessarily evaluate the safety and hence was moved as part of participant disposition which is in alignment with AZ standard shells reporting.
- CCI [REDACTED].
- The definition of the treatment emergent AEs was clarified to account for instances where a participant withdraws from the study over a phone call and disposition (DS) page in eCRF is populated without the corresponding visit being recorded. In addition, the change in relationship was removed as pre-treatment AE that changes the relationship would need to be entered in the database as a new AE with a start date on or after the first IP administration date and hence would automatically become a treatment emergent AE as per the first part of the definition.
- Other secondary endpoints, DSIS and rescue medication use will be summarised and analysed using available data on protocol specified visits and not just those visits specified in the definition of the endpoint itself (Week 2, 4, 6, 8, 10, 12 and 18).

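### The post-treatment period closes at the last study assessment while TEAEs run to the DS-page end of participation, so TEAEs with late onset before a phone withdrawal may belong to no exposure period

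*SAP*

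**What the plan says.** Three statements in the SAP fix which period an adverse event belongs to.

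- Section 3.1.6.2: "On treatment is defined from the day and time of first IP administration throughout to the last IP administration +14 days".
- Section 3.1.6.3: "Post treatment is defined from last IP+15 days through to the date of last study assessment".
- Section 3.6.1 makes an event a TEAE if it starts, or worsens, at the time of or "following the start of study treatment through the end of study participation as per DS page in eCRF".

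Section 6 gives the reason for the last wording. The TEAE definition was clarified for cases where "a participant withdraws from the study over a phone call and disposition (DS) page in eCRF is populated without the corresponding visit being recorded". Section 3.1.6.3 carries no matching wording.

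Section 4.2.6.1 joins the two definitions. "Summary tables will include TEAEs as defined in section 3.6.1, unless otherwise specified", and several of those tables are split "By periods as defined in section 3.1.6": AEs, severe AEs, causally related AEs and SAEs, SAEs, and AESIs (overall and by category). Under the AESI item it adds: "Joint related AESI table by study periods will also include the exposure adjusted rates".

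Section 3.1.5 separately defines study periods. Its follow-up period (3.1.5.3) ends with the end of study participation.

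**The concern.** The SAP recognises that the last recorded visit and the end of participation can differ, and it set the TEAE end date to allow for that. The period definition that classifies the same events was left on the earlier date. When the two dates separate, an event can be treatment-emergent and yet be neither on treatment nor post treatment. No residual category is defined for it.

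The tables exposed include the by-period SAE and AESI tables. The gap can only arise late in a participant's follow-up, and only in participants who leave without a closing visit. Where it does arise, the period columns will not reconcile with the overall TEAE table, and the post-treatment column will be the one that is short.

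**Working it through.** The SAP gives no figure to reproduce here, so the check applies the rules literally to example records.

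**Rules**

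- On treatment: first dose ≤ onset ≤ last IP + 14 (section 3.1.6.2).
- Post treatment: last IP + 15 ≤ onset ≤ last study assessment (section 3.1.6.3).
- TEAE: first dose ≤ onset ≤ DS-page end of participation (section 3.6.1).
- Unassigned TEAE: onset > max(last IP + 14, last study assessment) and onset ≤ DS date.
- Number of unassigned days: DS date − max(last IP + 14, last study assessment), or 0 if negative.

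**Example records.** The day numbers are assumptions chosen to show the mechanism.

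| Case | Last IP | Last IP + 14 | Last assessment | DS date | Unassigned onset days |
|---|---|---|---|---|---|
| (a) All doses given, withdrawal by phone in follow-up | 71 | 85 | 127 | 160 | 128 to 160: 160 − 127 = 33 |
| (b) Early stop with ET visit, later phone withdrawal | 29 | 43 | 43 | 60 | 44 to 60: 60 − 43 = 17 |
| (c) Phone withdrawal soon after last dose | 29 | 43 | 29 | 40 | 0, because Day 40 is within last IP + 14 |
| (d) As (a), with the call counted as an assessment | 71 | 85 | 160 | 160 | 0 |

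In (a), an event with onset on Day 120 that the participant first mentions on the Day 160 call is still classed as post treatment, since 86 ≤ 120 ≤ 127. Onset date decides the period; the way the event was reported does not.

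If section 3.1.6.3 ended at the DS date, the unassigned days in (a) and (b) would also be 0.

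**Joint AESI rate.** The sentence that introduces the rate refers to study periods, which is the heading of section 3.1.5. It is nested under a bullet that cites section 3.1.6.

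- Under 3.1.5, follow-up runs to the end of participation and the events are kept.
- Under 3.1.6, they are lost from the numerator. Section 4.2.6.1 divides by days at risk without saying when those days end. If they stop at the last assessment, the matching time is dropped too and the direction of the effect is unclear. If they run to the DS date, the rate is understated.

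**The case against.** The case against giving this much weight has four parts.

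1. **A call may be a study assessment.** Section 3.1.6 describes its periods in terms of safety assessments, section 3.6 lists AEs among the safety variables, section 3.6.1.2 collects AEs by an open question from site staff, and section 1.2 schedules four follow-up calls. On that reading the gap is zero, as in case (d). This stands as a possibility. The wording in section 6 about no visit being recorded makes it less likely but does not exclude it, and a programmer would have to choose.

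2. **No event disappears from the report.** The events stay in the overall TEAE, SAE and AESI tables, the table of adjudicated joint events and the AE, SAE and AESI listings, and the safety summaries are descriptive only (section 4.2.6). This stands in full. The by-period tables are what is damaged.

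3. **Joint events are partly protected.** Joint AESIs must be positively adjudicated (section 3.6.1.1), and section 3.6.10 provides for-cause imaging. Study imaging after onset would be an assessment and would move the end of the period past the onset. An unassigned joint event would therefore need to be adjudicated with no later study assessment, for example from imaging done outside the study.

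4. **Stronger readings are tempting but unsupported.** A reader might infer that everything reported on a withdrawal call is lost, that every by-period safety table is affected, or that the joint AESI rate necessarily omits these events. Onset date governs assignment, so the first does not follow. The other two depend on which periods the joint rate table uses, which the SAP leaves open. A reader might also size the gap at 97 days (224 − 126 − 1, between nominal Week 18 and Week 32). That is a worst case: it assumes no assessment in between and ignores any scheduled call that counts as one.

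**Conclusion.** The two end dates disagree, and the case in which they separate is the one section 6 names. Read literally, and provided the withdrawal call is not itself a study assessment, TEAEs with onset after both last IP+14 days and the last study assessment are left out of the section 3.1.6 by-period AE, severe AE, causally related AE and SAE, SAE and AESI tables. An effect on the joint AESI exposure-adjusted rate is conditional on that table using the 3.1.6 periods.

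The size cannot be derived from the SAP, which gives neither the number of phone withdrawals nor the expected number of events. Assuming that 2% to 8% of 350 participants withdraw this way gives 7 to 28 participants (0.02 × 350 and 0.08 × 350). Those percentages have no source in the document, and they count participants with a gap rather than participants with an event in it. Likewise, a 20% change in an arm's joint event rate needs one event lost out of five with the days at risk unchanged, and the SAP supports neither premise. The number of affected events is probably small.

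The point is still worth correcting because a stated rule misclassifies events in serious-event and special-interest tables, and the correction is simple.

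**What to change.** - In section 3.1.6.3, end the post-treatment period at the end of study participation as recorded on the DS page. This matches section 3.6.1 and agrees with the end of follow-up in section 3.1.5.3. It also removes the need to decide whether a call is a study assessment.
- End the post-treatment days at risk on the same date, so that numerator and denominator of any period-specific rate cover the same time.
- In section 4.2.6.1, state whether the joint AESI table with exposure-adjusted rates uses the periods of section 3.1.5 or of section 3.1.6.

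The cost is a sentence or two in the SAP and one period end-date variable in the analysis datasets. No new data are needed.
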